3.1.3 Visit 3: Post-Operative Visit (14 days \pm 2 days)

The stage of healing will be clinically assessed. Remaining suture material will be removed. Buccal and crestal photographs of the surgical site will be obtained using a Canon 50D digital camera body with a Canon 100mm f/2.8 macro lens and a Canon MR-14EX macro ring flash.

AEs/ADEs will be recorded.

This visit is standard clinical protocol

3.1.4 Visit 4: Cone Beam Computed Tomography Imaging (12 weeks \pm 7 days)

Small field-of-view cone beam computed tomography (CBCT) imaging whilst wearing the radiographic stent will be obtained for all patients 3 months following surgical treatment. Images will provide post-ridge preservation data for horizontal and vertical bone assessments. Buccal and crestal photographs of the surgical site will be obtained. An elastomeric impression of the site will be obtained.

AEs/ ADEs will be recorded.

This appointment contains a CBCT, photographs and an impression which is standard clinical protocol when planning future implant placement. Additionally the CBCT and impression will be used for research purposes.

Additional visits may be scheduled at the discretion of the investigator and recorded as extra visits in the CRF.

Figure 3 Appointment flow chart

[figure not shown]

Table 1 Study plan

Visit Number	1	2	3	4
Visit Description	Screening, Impressions	Extraction, initial CBCT, Ridge Preservation	Post-op	Post-op, Impressions, final CBCT
Visit Window		0	2w	12w
Patient Information				
Informed consent	X (R)			
Patient demographics	X (C)			
Medical/surgical history	X, (C)			
Oral examination	X (C)			
Inclusion/exclusion criteria	X (R)			
Radiographic examination	X (C)			
Treatment				
CBCT		X (R)		X (C)
Clinical photography		X (C)	X (C)	X (C)
Tooth Extraction		X (C)		
Site Preservation		X (C)		
Suture removal			X (C)	
Impression	X (C)			X (C)
Other				
Adverse events/Adverse device effects		X	X	X
Summary of additional patient requirements per appointment solely for research purposes		CBCT		

**All standard of care procedures will be used for research purposes.

Standard of Care Clinical requirement=C

Research requirement =R

3.2 Rationale and risk/benefit assessment

Limited data is available regarding volumetric changes of the alveolus following tooth extraction and ridge preservation procedures. This has direct effects on subsequent dental implant treatment. Successful ridge preservation enhances proper implant placement. Furthermore, it is necessary to better define the effects of different grafting materials on the clinical outcomes following ridge preservation. This study has been designed to treat a clinical scenario commonly encountered in clinical practice

The public will benefit from the study results, which will help to define the knowledge of bone healing following extraction and ridge preservation with different grafting materials. This will help aid clinicians in the selection of materials to optimize their clinical outcomes of treatment. It will also further characterize the effects of these materials on soft tissue healing while comparing its outcomes to other commonly used materials. Data acquisition includes minimally invasive collection methods, both before and after the extraction and ridge preservation procedure.

3.2.1 Study selection record

Investigator(s) will keep a record of subjects who were considered for enrollment but were never enrolled (e.g., subject screening log). This information is necessary to establish that the subject population was selected without bias.

3.2.2 Inclusion criteria

For inclusion in the study subjects must fulfill all of the following criteria:

1. Provision of informed consent
2. ≥ 18 years and ≤ 75 years
3. Good physical health (ASAI/II)
4. Extraction of maxillary premolar, canine or incisor, or mandibular premolar and canine required (4-13, 20-22, 27-29)
5. Teeth adjacent (mesial and distal) to study site must consist of two stable natural teeth with minimal restorations, without signs of periodontal bone loss (> 3 mm) and/or significant soft tissue deficiencies

3.2.3 Exclusion criteria

Any of the following is regarded as a criterion for exclusion from the study:

1. Buccal plate dehiscence and/or fenestration >3 mm at study site following extraction
2. Untreated rampant caries and uncontrolled periodontal disease
3. Inadequate oral hygiene (estimated plaque score $>20\%$)

4. Smokers using more than 10 cigarettes or equivalent per day
5. Smokeless tobacco use or e-cigarette use
6. Compromised physical health and/or uncontrolled or severe systemic diseases including:

ASA III/IV

Metabolic bone disease

History of malignancy

History or radiotherapy or chemotherapy for malignancy in the past 5 years

History of autoimmune disease

Long-term steroid (20mg cortisol or equivalent for 2 weeks duration in past 2 years) or antibiotic therapy (Antibiotic therapy exceeding 2 weeks in past 1 year)

Uncontrolled diabetes (HbA1c ≥ 7)

Known alcohol or drug abuse

7. Systemic or local disease or condition that would compromise post-operative healing
8. Use of any substance or medication that will influence bone metabolism
9. Pregnancy at time of screening
10. Unable or unwilling to return for follow-up visits for a period of 3 months
11. Unlikely to be able to comply with study procedures according to Investigators judgement
12. Involvement in the planning and conduct of the study
13. Previous enrolment or randomization of treatment in the present study

3.2.4 Restrictions

Subjects will be advised of the following restrictions during the study period:

- To avoid disruption of wound healing during the initial study period the subject should have a restricted diet for at least 3-5 days and will be instructed to avoid manual oral hygiene in site for 2 weeks (printed instructions will be distributed to the subjects at Visit 2)
- For current smokers, interim cessation will be encouraged and no more than 10 cigarettes per day are allowed

3.2.5 Discontinuation of subjects from treatment or assessment

3.2.5.1 Criteria for discontinuation

Subjects may be discontinued from study treatment and assessments at any time. Specific reasons for discontinuing a subject from this study are:

- Voluntary discontinuation by the subject who is at any time free to discontinue his/her participation in the study, without prejudice to further treatment
- Safety reasons as judged by the investigator
- Severe non-compliance to protocol as judged by the investigator
- Incorrect enrolment (i.e., the subject does not meet the required inclusion/exclusion criteria for the study)
- Subject received further dental therapy on study site or adjacent teeth without consent of investigator (e.g. new crown, periodontal surgery, or orthodontics on adjacent teeth)
- Subject lost to follow-up

3.2.5.2 Procedures for discontinuation

Subjects who discontinue should always be asked about the reason(s) for their discontinuation and the presence of any AEs or ADEs. If possible, they should be seen and assessed by an investigator(s). Ongoing AEs and ADEs should be followed up.

A subject will be classified as lost to follow up only if, he/she has failed to return to the required study visits and his/her dental status remains unknown, despite multiple attempts to contact the subject via telephone, fax, email, certified letter and through subject locator agencies (if allowed per national regulation).

3.3 Treatments

3.3.1 Identity of investigational product and comparators

All procedures involved in this research study are standard of care procedures for patients requiring dental extraction and desiring dental implant treatment in the future. All graft materials and their combinations used in this study are widely used in the dental procession for patient care. All components are commercially available.

Symbios demineralized cortical-cancellous granule mix is a human allograft product obtained from the Musculoskeletal Transplant Foundation (MTF), which mimics the natural bone anatomy, providing space maintenance and surface area for bone formation. The material contains 80% cortical and 20% cancellous bone, displaying a particle size of 200-1000 microns.

Symbios OsteoGraf LD-300 is a 100% pure synthetic hydroxyapatite bone product that shows 56% porosity and high surface area. It is conducive to solution-mediated resorption, producing a readily available source of calcium for bone regeneration. This low density resorbable grafting material presents as 250-420 micron particles, and is available in 0.5, 1.0 and 3.0 gram vials.

Symbios OsteoGraf/N – 300 is a sintered natural anorganic bovine-derived microporous hydroxyapatite, displaying a particle size of 250-420 microns. The hydroxyapatite is conducive to cell-mediated resorption and provides a scaffold for new bone growth, holding the space until host bone takes over. There are no extractable proteins present in the product. The product is available in 1.0 and 3.0 gram vials.

Symbios OsteoShield Collagen Resorbable membrane made from Type-I bovine collagen from the Achilles tendon. It has a resorption time of between 26 and 38 weeks. It is a multi-layered membrane, which assists in healing of the bone and surrounding tissues, while the inner layers help prevent cellular and bacterial down growth. The membrane is available in 15x20mm, 20x30mm and 30x40mm.

3.3.2 Labeling

All grafting materials and membranes will be labelled as follows:

- “Reference number”
- “Lot number”
- “Expiration date”

The reference number and lot numbers will be recorded in clinical records (source data) and CRF.

3.3.3 Storage

All investigational products must be kept in a secure place under appropriate storage conditions. A description of the appropriate storage and shipment conditions are specified on the study product label and product information.

3.3.4 Accountability

Distributed study products will be used for this study in accordance with the Clinical Study Protocol. All product deliveries will be confirmed by the investigator or delegate.

3.4 Method of assigning subjects to treatment groups

Subject numbers (subject ID) will be consecutively allocated in series at day of inclusion (Visit 1). Subjects will receive numbers starting at 101. Enrollment will continue until 80 subjects have been allocated a subject ID. If a subject discontinues, the subject number will not be reused.

Subjects will be randomized strictly sequentially at day of extraction and ridge preservation (Visit 2). At Visit 2 all study sites in all subjects are considered equivalent. The randomization schedule will be generated using a validated system under the responsibility of the investigatory team. 80 pieces of folded paper will contain the allocated treatment group (20 each of group A, B, C and D) and contained in an enclosed container. One piece of paper will be blindly selected by the PI or co-investigators, and the treatment group will be revealed to the clinician only following extraction of the tooth.

The randomization code papers will be stored in an enclosed and concealed container and stored by PI and co-investigators.

3.5 Pre-study, concomitant and post-study treatment(s)

In the case of dehiscence, fenestration, infection, or other surgical complications encountered during treatment and/or healing, appropriate site preservation procedures and/or debridement and/or infection control steps will be implemented.

4 MEASUREMENTS OF STUDY VARIABLES AND DEFINITIONS OF OUTCOME VARIABLES

4.1 Screening and demographic measurements

The following data will be recorded via a standard CRF:

- Date of birth
- Height and weight (Body Mass Index)
- Sex
- Race
- Relevant medical and surgical history
- Medication
- Oral examination
 - Periodontal disease
 - Bone loss
 - Caries
 - Mobility
 - Crown
 - Post/core
 - Endodontic treatment
 - Existing periapical radiolucency
- Tobacco use
- Reason for tooth extraction
- Previous bone graft, soft tissue graft, or apical surgery

4.2 Efficacy

4.2.1 Primary outcome variable

4.2.1.1 Volumetric osseous changes

The amount of change in bone volume will be calculated using data from DICOM images acquired by CBCT using 3D software.

4.2.1.1.1 Methods of assessment

CBCT images will be obtained at baseline (Visit 2) and 3 months following alveolar ridge augmentation (Visit 4). Using 3D imaging software, the bone will be segmented to produce an STL file. Following this, the segmented images will be superimposed and aligned through a fiducial point registration algorithm, and at the same time, the same region of interest will be cropped in each scan and exported as a separate model. The volume of the baseline and 3 month scan will be calculated and compared.

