A circumferential sulcular incision will be placed around the teeth to be extracted. Periotomes and luxators will be used to extract the tooth with minimal trauma to the adjacent tissues. The socket wall will be examined for any dehiscence greater than 3mm or fenestrations. If these are present, the patient will be excluded from the study. Gauze will be placed in the area to produce wound hemostasis

Immediately following tooth extraction, the patient will have a small field-of-view cone beam computed tomography (CBCT) image produced whilst wearing the radiographic stent. Images will provide pre-preservation data for horizontal and vertical bone locations.

Following CBCT imaging, a ridge preservation procedure will be completed as follows:

- Group A: Symbios demineralized cortical-cancellous granule mix reconstituted in sterile saline will be used to augment the socket and will be covered by a Symbios OsteoShield Collagen resorbable membrane.
- Group B: Symbios OsteoGraf LD-300 reconstituted in sterile saline will be used to augment the socket and will be covered by a Symbios OsteoShield Collagen resorbable membrane.
- Group C: Symbios OsteoGraf/N-300 reconstituted in sterile saline will be used to augment the socket and will be covered by a Symbios OsteoShield Collagen resorbable membrane
- Group D: Socket covered with Symbios OsteoShield Collagen resorbable membrane and no grafting material, allowing socket to heal.

Grafted sockets will be closed with a barrier membrane using 5-0 chromic gut suture. It is anticipated that a cross mattress and/or simple loop sutures will be employed.

All surgical procedures listed above are standard clinical procedures, including preparation and utilization of grafting materials list above.

Post-Surgical Procedures

Buccal and crestal photographs of the surgical site will be obtained, which is standard clinical practice in the School of Dentistry.

Standard UNC post-operative instructions will be given which includes the use of a Chlorhexidine rinse 2 times daily for 2 weeks.

This visit includes a CBCT for research purposes only. The remainder of treatment is standard clinical protocol.

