4.2.1.1.2 Derivation or calculation of variable

The changes in the bone volume between baseline (Visit 2) and 3 months (Visit 4) will be measured electronically using 3D analysis software. The change for each study site will be compared longitudinally and the average for each treatment group will be calculated and compared among treatment and control groups.

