4.2.2.2 Soft tissue dimensional change

The amount of soft tissue change will be assessed through the use of dental casts at two time points following extraction and ridge preservation, and 3 months.

4.2.2.2.1 *Methods of assessment*

Elastomeric impressions will be made of the site at baseline, and 3 months following extraction. The impression will be poured in dental stone, and the cast will be scanned using an optical/laser scanner to produce a digitized model. The digital models will then be aligned in 3D software and superimposed on one another and the relevant CBCT image utilizing the fiducial point registration algorithm.

4.2.2.2.2 *Derivation or calculation of variable*

The mid-alveolar point (middle of the extraction site) positioned on a tangent drawn from the mesial and distal adjacent tooth CEJs will be used as a reference point for assessment of dimensional bone changes in the Z-axis (soft tissue width) at 3, 6 and 9mm as measured from the height of the original buccal zenith and indicated on the radiographic stent. Measurements will be taken from at these points from the buccal contour to the underlying buccal plate. Changes in the Y-axis (soft tissue height) will also be assessed. The changes in the soft tissue dimensions between baseline (Visit 2) and 3 months (Visit 4) will be measured. The change for each study site will be compared longitudinally and the average for each treatment group will be calculated and compared among treatment groups.

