6.3 Determination of sample size

A sample size of 20 participants per treatment group was selected following power calculations and allowing for 10% patient dropout (has dropout rate been factored into our sample size of 20 patients per group). A sample size of 18 patients was calculated for the primary outcome variable (horizontal bone changes) with the assumption that the detectable difference would amount to 0.5mm³ with a standard deviation of 0.5. The type I error probability was set at 0.05 and the statistical power was set at 80%.

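### The plan does not mask whoever reads the CBCT scans and casts to treatment group, and it fixes no segmentation threshold, so reader expectation could enter the primary volumetric outcome

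*Combined protocol and SAP*

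**What the plan says.** **Primary outcome (4.2.1.1.1, 4.2.1.1.2).** "Using 3D imaging software, the bone will be segmented to produce an STL file". The two scans are superimposed, and "the same region of interest will be cropped in each scan and exported as a separate model". The volume change "will be measured electronically using 3D analysis software". No reader is named, no threshold or crop boundary is given, and no repeat reading is planned.

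**Linear bone outcomes (4.2.2.1).** Width is measured on registered CBCT images at 3, 6 and 9 mm from the original buccal zenith, and height is also measured. The reader is not named.

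**Soft-tissue outcomes (4.2.2.2).** Impressions are poured, and "the cast will be scanned using an optical/laser scanner to produce a digitized model". The models are superimposed on each other and on the CBCT. Again no reader is named.

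**Who knows the group (3.1.2, 3.4).** The draw is described as follows: "One piece of paper will be blindly selected by the PI or co-investigators". The PI and co-investigators also store the papers. Concealment ends at surgery, since "the treatment group will be revealed to the clinician only following extraction of the tooth". The only blinding language in the available text concerns the draw. At surgery, group D is plainly different: "Socket covered with Symbios OsteoShield Collagen resorbable membrane and no grafting material".

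**Stated expectation (2.1).** No difference is anticipated among the three graft groups. Graft plus membrane is expected to hold more ridge volume than membrane alone.

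**The concern.** Setting a bone boundary on CBCT, choosing registration points and placing a crop leave room for judgement unless a rule removes it, and the plan gives no such rule. The people who draw the allocation and treat the patient are not kept away from the measurement, and the files are not coded. A reader who knows the group and shares the written expectation could, without intending to, draw the boundary slightly differently in grafted and ungrafted sites.

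Such a difference would add directly to the between-group difference in volume change. The most exposed planned primary test is A versus D, the only one of the three tests in 6.2.1 that compares a graft with membrane alone. The expectation of no difference among grafts gives no similar push towards false positives in A versus B or A versus C.

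**Working it through.** **1. Is masking provided anywhere?** Setting the relevant sections side by side:

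| Section | Step | Masking of reader |
|---|---|---|
| 2.1, 4.2.1.1 | Segment, register, crop, compute volume (primary) | Not stated |
| 4.2.2.1 | Linear bone width and height (secondary) | Not stated |
| 4.2.2.2 | Cast scan, superimposition, soft-tissue width and height (secondary) | Not stated |
| 3.1.2, 3.4 | Draw of the allocation paper | Draw is blind; group is then known to the clinician |

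A reader who knows the group would therefore comply fully with the plan as written.

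**2. What do the existing safeguards do?** The radiographic stent (3.1.1) fixes alignment and measurement points. Registration and a common region limit how far the two crops can drift apart. Electronic measurement removes arithmetic discretion. All of these make readings more uniform. None hides the group, and none fixes where bone ends in the segmentation.

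**3. The plan's own sample size (6.3).** Inputs: difference 0.5, SD 0.5, so a standardised effect of 0.5/0.5 = 1.0. "The type I error probability was set at 0.05 and the statistical power was set at 80"%. The two-sided form comes from the alternative hypothesis in 6.2.1.
- Normal formula: n = 2(1.960 + 0.842)² / 1.0² = 15.70, so 16 per group.
- Two-sample t-test: 16.71, so 17.
- t-test n divided by the Wilcoxon efficiency of 0.955 under normality: 16.71/0.955 = 17.50, so 18. This matches the plan.
- Dropout: 18/0.90 = 20 per group, also matching.

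Masking the reader changes none of these numbers.

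**4. Illustration of a reader shift.** The documents give no reader-error figure, so the shift δ (in SD units) is an assumption. Setting: no true difference, normal data, n = 18 per group, two-sided Wilcoxon test at 0.05.

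Normal approximation: d = δ/√(2/18) = 3δ, and the rejection rate is 1 − Φ(1.96 − d) + Φ(−1.96 − d).

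| δ (SD) | d | Normal approximation | Simulated Wilcoxon |
|---|---|---|---|
| 0 | 0 | 5.0% | 4.8% |
| 0.1 | 0.3 | 6.0% | 5.4% to 5.5% |
| 0.2 | 0.6 | 9.2% | 8.1% to 8.5% |
| 0.4 | 1.2 | 22.4% | 19.8% to 20.1% |

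The ranges are the spread across repeated simulation runs, where run size was recorded 20,000 or 40,000 replicates. The table is kept in SD units because 6.3 calls the primary variable horizontal bone change but prints the difference in mm³, while the synopsis and 4.2.1 make the primary outcome volumetric. A shift in millimetres would not describe the primary outcome.

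**The case against.** **The reading is already standardised.** The stent, registration and common region do limit crop-driven differences, and this stands. They do not hide the group, and the bone boundary is still not set by a stated rule.

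**Masking helps least where it matters most.** The baseline scan precedes grafting, so its image carries no graft information, and the casts do not feed the primary outcome. The 3-month scan may show graft particles. This also stands in part: masking of the primary outcome may be incomplete. It is why the threshold and crop should be fixed on the pre-graft scan, which limits discretion even where masking fails.

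**Silence is not a plan to read unmasked.** Correct. A reader might infer that the treating clinicians will do the segmenting or that the trial is declared open. The documents say neither. Section 6.1 mentions a Data Management Plan and an optional SAP that were not supplied, and the flow charts and one part of the protocol were not available. What can be said is that the available text does not require masking.

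**Not every outcome rests on segmentation.** A reader might also infer that it does, or that the casts bear on the primary result. Segmentation and cropping are described only for the volumetric outcome, and casts serve only the secondary soft-tissue outcome.

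**Conclusion.** The gap is real and worth closing. As written, the plan allows a reader who knows the group to segment, register and crop the scans behind the primary outcome, with no fixed threshold and a stated expectation favouring graft over membrane alone. The same lack of masking applies to the linear bone and soft-tissue measurements.

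The size and direction of any bias cannot be derived from the documents. The illustration says only that an unnoticed shift acts like a treatment effect: negligible at 0.1 SD, about 8% false positives at 0.2 SD and about 20% at 0.4 SD, for one test at 18 per group under normality. It would be wrong to read 20% as this trial's error rate, or to conclude that the results are biased. This is a risk of unknown size that can be reduced cheaply.

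**What to change.** Add to 4.2.1.1.1, 4.2.2.1.1 and 4.2.2.2.1:

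- The study coordinator replaces subject identity and group with random codes on all scans and cast files before reading.
- Scans and casts are read in random subject order by a listed co-investigator who neither operated on that subject nor drew that subject's allocation.
- For the volumetric outcome, the segmentation threshold and crop region are fixed on the pre-graft baseline scan and applied unchanged to the registered 3-month scan. Group is masked under this procedure; visit is not.
- The wording in 4.2.1.1.1 that has both scans cropped during alignment is amended to match this order.
- The protocol states that masking may be partial where graft particles are visible at 3 months.

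**Cost.** Modest coordinator time and a short written procedure, using staff already listed. There are no extra visits, subjects or scans, and the sample size is unchanged. The remaining weakness is incomplete masking of some 3-month scans.

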2 STUDY OBJECTIVES

2.1 Primary objective

The primary objective is to compare the volumetric changes in the osseous dimensions following a post-extraction ridge preservation procedure. Three different bone-grafting materials will be used, along with comparison to a non-grafted membrane only group. Data will primarily be obtained from DICOM images acquired by CBCT imaging. A surface based model will be constructed through image segmentation from both the pre- and post-operative CBCT images. The models will then be aligned/superimposed using a surface registration algorithm. Both images will be cropped to represent the same region of interest and the volumes will be calculated and compared.

Hypothesis: No significant differences in ridge volume maintenance are anticipated among the three grafting groups. The combined use of particulate graft material with a resorbable collagen membrane will maintain a greater ridge volume than the use of a resorbable collagen membrane alone.

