3.1.1 Visit 1: Screening

Subjects in need of a single tooth extraction and ridge preservation of a single tooth bound by adjacent teeth that are deemed eligible by meeting inclusion and exclusion criteria will be considered for treatment in this study. The tooth requiring extraction must lie within the region 4-13, 20-22, 27-29 (maxillary or mandibular first premolar or anterior tooth, excluding mandibular incisors).

Before any assessment or examination is carried out the subject must have been informed orally and in writing about the study, and have signed the appropriate clinical and study consent forms. Informed consent for the research study will be given and signed on paper, as well as HIPAA authorization. Subjects will also be asked to sign informed consent documents.

Individuals meeting all inclusion and exclusion criteria and that have signed all appropriate consent forms will be further evaluated. A clinical exam will entail evaluation of general dental and systemic health. It will also include a clinical and radiographic assessment of the tooth to be removed and the adjacent teeth, which is standard of care. Pre-existing radiographs (e.g. panoramic and intraoral) can be used but must not be older than 6 months. An impression will be made using an elastomeric impression material of the planned extraction site to allow fabrication of a temporary tooth (standard clinical requirement). This impression will also serve an additional research purpose, providing baseline tissue data. Subjects will immediately be scheduled for Visit 2 provided that they fulfill all inclusion and exclusion criterion.

A radiographic stent for research purposes will be fabricated using the model obtained from the initial impression to aid in image alignment, superimposition and identifying the points of measurement for the study objectives.

After pre-surgical evaluation and planning, patients will be enrolled and randomly allocated treatment into treatment group A, B, or C; or into group D.

[figure not shown]
This visit includes all procedures, which are standard clinical protocol, with additional usage of the clinical impression for research purposes.

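### The region of interest for the primary bone volume has no stated limits and is cropped on the superimposed scan pair; it should be fixed on the pre-graft Visit 2 scan

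*Combined protocol and SAP*

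**What the plan says.** Section 4.2.1.1 defines the primary outcome: "The amount of change in bone volume will be calculated using data from DICOM images acquired by CBCT using 3D software". Section 4.2.1.1.1 segments both scans, after which "the segmented images will be superimposed and aligned through a fiducial point registration algorithm" and, in the same sentence, "at the same time, the same region of interest will be cropped in each scan and exported as a separate model". Section 2.1 gives the same order with a different alignment method: "The models will then be aligned/superimposed using a surface registration algorithm", then "Both images will be cropped to represent the same region of interest and the volumes will be calculated and compared". Section 4.2.1.1.2 adds only that "The change for each study site will be compared longitudinally and the average for each treatment group will be calculated". It does not say whether change is in mm³ or percent.

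None of these sections gives the region a landmark, a size, or a mesiodistal, coronal or apical limit. Either alignment method brings the scans together; neither bounds a volume.

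The secondary measures are better anchored. Sections 4.2.2.1.2 and 4.2.2.2.2 use a tangent between the adjacent teeth's CEJs, the mid-alveolar point on it, and levels 3, 6 and 9 mm from the original buccal zenith. The stent in section 3.1.1 is made "to aid in image alignment, superimposition and identifying the points of measurement for the study objectives".

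On timing, section 3.1.2 states: "Immediately following tooth extraction, the patient will have a small field-of-view cone beam computed tomography (CBCT) image produced". Grafting follows that scan. Blinding language appears only for the allocation draw (sections 3.1.2 and 3.4). No reader masking, second reader or repeatability check is stated.

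**The concern.** Using one region for both scans removes bone that has not changed. It does not remove the effect of the region's own size on the difference between the scans. The plan fixes the geometry of its secondary linear measures and leaves open that of the primary outcome, so two competent readers could follow the text on the same scans and report different changes.

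Two harms are possible. If the extent varies haphazardly between subjects, it adds noise to a trial planned at 80% power with 18 evaluable subjects per group. If the extent differs systematically between arms, it can produce a group difference where none exists. The second harm requires that whoever crops knows the allocation or infers it from graft visible at 3 months.

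**Working it through.** **The plan's own figure.** Section 6.3 uses a difference of 0.5, SD 0.5, alpha 0.05 and 80% power. The normal approximation gives 16 per group. The t-test gives 16.7; divided by the Wilcoxon efficiency of 0.955 this is 17.5, so 18, as stated. Then 18/0.90 = 20 per group. The stated size reproduces. The same section calls the primary variable horizontal bone change yet gives the difference in mm³, so its SD cannot be tied to any region volume. The work below is therefore in SD units.

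**Geometry (assumed dimensions).**
- Absolute change, loss running to the box edge: loss = depth × height × box length. For 1 mm lost over 8 mm of height, a 5 mm box gives 1 × 8 × 5 = 40 mm³ and a 7 mm box gives 1 × 8 × 7 = 56 mm³. The same resorption reads 56/40 = 1.4 times as large.
- Percent change, box length: for a ridge 8 mm wide, 40/(8 × 8 × 5) = 12.5% and 56/(8 × 8 × 7) = 12.5%. Length cancels.
- Percent change, apical extent: take a ridge 8 mm wide and 7 mm long that loses 1 mm over its coronal 6 mm. The loss is 1 × 6 × 7 = 42 mm³. In a 6 mm high box this is 42/336 = 12.5%; in a 15 mm box it is 42/840 = 5.0%. Absolute change is 42 mm³ in both.

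Each scale depends on a dimension the plan leaves open.

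**Noise.** Suppose each subject's change (mean loss m, SD 1) is multiplied by an independent box factor with mean 1 and coefficient of variation CV. The variance becomes 1 + CV² + m²CV². For arms averaging 1 and 2 SD of loss and CV 30%, the variances are 1.18 and 1.45, the pooled SD is √1.315 = 1.147, and a true difference of 1 SD shrinks to 1/1.147 = 0.87 SD. Simulated power (18 per group, two-sided Wilcoxon at 0.05, true difference 1 SD):

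| Mean loss in the two arms | No box variation | CV 20% | CV 30% |
|---|---|---|---|
| 1 and 2 SD | about 80% | about 75% | about 71% |
| 2 and 3 SD | about 80% | about 71% | about 59% |

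**Extent that follows visible loss only.** With no true difference and the same loss-dependent rule in both arms, the arms stay exchangeable. Simulated rejection was 4.5% to 5.1%, so the 5% level holds.

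**Extent that differs by arm.** With no true difference and one arm's changes multiplied by the factor shown, the simulated type I error is:

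| Mean loss | Box 10% longer | 20% longer | 30% longer |
|---|---|---|---|
| 1 SD | about 6% | about 8% | about 12% |
| 2 SD | about 8% | about 18% | about 31% |

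Repeat simulations agreed to within about one percentage point.

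**The case against.** A reader might infer that the person cropping sizes the outcome after seeing how much bone was lost, and that this alone creates a false difference between groups. The documents do not support that. They do not say who crops, whether cropping is manual, or whether the loss is inspected first. Cropping at the same time as alignment can equally be read as one simultaneous cut that guarantees identical limits. Even if loss were seen, cropping that depends on loss alone keeps the 5% level. It could alter the size of a true difference, but it does not create one. For the same reason it would be wrong to say that masking could not help: for false positives, dependence on arm is the necessary ingredient. Whether graft is recognisable at 3 months is not described.

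It is also fair to say that the 40% example assumes absolute change, which is not stated, and that absolute change does not depend on box size once the box encloses all the loss. This stands as a limit on the size of the problem, but the plan does not require enclosure.

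Finally, the stent serves all study objectives, and the site is a single tooth between neighbours, which restrains mesiodistal extent in practice. This helps, but the stent supports alignment and points of measurement. Neither it nor the adjacent teeth are given as limits of the volume.

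**Conclusion.** The point holds as an under-specified primary measurement with a better method readily available. The order of steps and the absence of limits are plain in sections 2.1 and 4.2.1.1 to 4.2.1.1.2.

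The more general harm is lost power: from about 80% to between about 75% and 59% over the ranges examined. This rests on an assumed box-length CV of 20% to 30%, mean losses of 1 to 3 SD, and change analysed in absolute terms with loss reaching the box edge.

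Bias between groups is conditional. It needs the extent to differ by arm, through known allocation or visible graft, and nothing stated prevents that. If it did differ by 10% to 30%, type I error would be about 6% to 12% at a mean loss of 1 SD and 8% to 31% at 2 SD. The documents give no mean loss and no evidence of such a shift, so these are ranges under assumption and not predictions. The change should be made, but the plan as written is not shown to be biased.

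**What to change.** Amend sections 4.2.1.1.1 and 2.1 as follows.

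1. Set the region on the Visit 2 scan alone, before the Visit 4 scan is opened. That scan precedes grafting, so it shows neither graft nor outcome.
2. Define its mesiodistal, coronal and apical limits from landmarks already in the plan: the adjacent-tooth CEJ tangent, the mid-alveolar point and the stent levels.
3. Lock the region and carry it unchanged to the Visit 4 scan through the registration.
4. In section 4.2.1.1.2, state whether the analysed change is absolute or percent.

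It would also help to state that whoever sets the region is not told the allocation, since the Visit 2 scan hides the group only if it is not known from elsewhere.

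The cost is a change of order and about a paragraph in the imaging procedure, with no extra scan, reader or patient. The one drawback is that a stated exception is needed where an adjacent root intrudes or the site is too narrow for the set limits.
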